### **7.2 Subject Withdrawal of Consent**

The investigator/treating physician will make every reasonable effort to keep each subject on study. A subject may withdraw from the study at any time at his/her own request without penalty, at any time during the study. If the subject withdraws consent for disclosure of future information, the sponsor may retain and continue to use any data collected before such a withdrawal of consent. All subject samples that were obtained prior to subject withdrawal will NOT be destroyed and future laboratory testing will be performed.

### **7.3 Lost To Follow Up**

All reasonable efforts must be made to locate subjects to determine and report their ongoing status. This includes follow-up with persons authorized by the subject. Lost to

follow-up is defined by the inability to reach the subject after a minimum of three documented phone calls, faxes, or emails as well as lack of response by subject to one registered mail letter. All attempts should be documented in the subject's medical record. Should the subject continue to be unreachable, he/she will be considered to have withdrawn from the study.

If it is determined that the subject has died, the site will use permissible local methods to obtain the date and cause of death.

#### **7.4 Treatment Failure**

In order to reduce bias, if subjects require concomitant therapy (i.e. other injections), pain scores and subsequent treatment information will continue to be collected through the 1-year follow up after a subject is declared a treatment failure.

#### **7.5 Discontinuation of the Clinical Study**

The study may be prematurely discontinued by the Sponsor if deemed necessary for any reason. If for any reason the study is discontinued early, all subjects should complete the End of Study visit and be followed for 90 days for SAEs that were ongoing at the End of Study visit.

### **8.0 Study Assessments and Procedures**

Subjects will have follow-up exams at 1 week, 1 month, 3 months, 6 months, 9 months (telephone only) and 1 year. After subjects complete the screening and consent portion of the trial, the subjects will undergo pre-injection MRI and then an additional MRI at 6 and 12 months. Additionally, subjects will fill out PROs at each time point.

#### **8.1 Study Visit Assessments**

##### **8.1.1 Screening Visit (Visit 1)**

- Administer informed consent and HIPAA Authorization
- Collect demography
- Collect medical and surgical history
- Collect prior and concomitant medications
- Collect Knee Osteoarthritis History
- Review inclusion and exclusion criteria
- Focused knee assessment
- Perform vital signs
- Knee MRI (only if the subject is eligible for the study)
- Collect subject PROs
- Perform pregnancy test (on female subjects of childbearing potential)
- Blood Collection (safety labs)
- Once all screening assessments are complete and eligibility has been confirmed by the treating investigator, the subject may be randomized.
- Schedule the subject for the appropriate Treatment Visit procedure based on randomization

### 8.1.2 Treatment Visit (Visit 2, Day 0)

- Collect concomitant medications
- Focused knee assessment (if required, at the discretion of the treating investigator)
- Perform vital signs
- Assess adverse events
- Perform pregnancy test (on female subjects of childbearing potential)
- Confirm subject eligibility
- Study procedures (**depending on subject randomization**)
  1. Arm 1-BMAC Treatment: bone marrow aspiration, cell processing and product release criteria testing
  2. Arm 1-CSI Treatment: bone marrow aspiration, cell processing, product release criteria testing and CSI preparation
  3. Arm 2-SVF Treatment: lipoaspirate procedure, cell processing, and product release criteria testing
  4. Arm 2-CSI Treatment: lipoaspirate procedure, cell processing, product release criteria testing and CSI preparation
  5. Arm 3-UCT Treatment: dispense UCT-MSCs, dose preparation, and product release criteria testing
  6. Arm 3-CSI Treatment: CSI preparation
- Perform arthrocentesis and knee injection
- Process and store samples for cell characterization (details are described in the Laboratory Manual)
- Home physical therapy program to begin post procedure day 8, see Appendix 12.1. Instructions for at home physical therapy will be provided to the subject by the study staff.

### 8.1.3 Week 1 (Visit 3, Day 7)

- Collect concomitant medications and treatments
- Focused knee assessment, including observation of knee injection site
- Observation of harvest sites (subjects in Arm 1 and Arm 2)
- Perform vital signs
- Assess adverse events
- Review progress of the at home physical therapy plan and encourage compliance

### 8.1.4 Month 1 (Visit 4, Day 30)

- Collect concomitant medications and treatments
- Focused knee assessment, including observation of knee injection site
- Observation of harvest sites (subjects in Arm 1 and Arm 2)
- Perform vital signs
- PROs
- Assess adverse events
- Blood Collection (safety labs)
- Immunogenicity testing (Arm 3 only)
- Review the subject's at home physical therapy log for compliance

### **8.1.5 Month 3 (Visit 5, Day 90)**

- Collect concomitant medications and treatments
- Focused knee assessment
- Perform vital signs
- PROs
- Assess adverse events

### **8.1.6 Month 6 (Visit 6, Day 180)**

- Collect concomitant medications and treatments
- Focused knee assessment
- Perform vital signs
- MRI
- PROs
- Assess adverse events

### **8.1.7 Month 9 Phone Call (Visit 7, Day 270)**

- Collect concomitant medications and treatments
- PROs
- Assess adverse events

### **8.1.8 Month 12/ (Visit 8, Day 365)**

- Collect concomitant medications and treatments
- Focused knee assessment
- Perform vital signs
- MRI
- PROs
- Assess adverse events
- Immunogenicity testing (Arm 3 only)

### **8.1.9 Unscheduled Visits**

Unscheduled visits are allowed as needed and at the discretion of the treating investigator for more frequent follow-up than what is required in the protocol. The treating investigator will determine the appropriate assessments to be conducted during this visit based on the reason for the Unscheduled Visit. Data from the Unscheduled visits will be captured in the EDC.

### **8.1.10 End of Study Visit**

If for any reason the study is discontinued early (according to section 7.5), all subjects should complete the End of Study visit and be followed for 90 days for any SAEs that are ongoing at the End of Study visit. All AEs potentially related to study participation will be followed until resolution prior to study completion. Open AEs that are unrelated to the study participation will not be followed beyond subject's study completion. Assessments completed during this visit will be at the discretion of the treating investigator and what is best for the safety of the subjects. Data from end of study visit will be captured in the EDC.

## **8.2 Clinical Assessments and Procedures**

### **8.2.1 Informed consent and HIPAA Authorization**

All subjects must agree to participate by signing and dating the informed consent and HIPAA Authorization prior to any study specific screening procedures being performed.

Consent must be documented by the subject's dated signature on a consent and HIPAA form along with the dated signature of the person conducting the consent discussion.

A copy of the signed and dated consent form and HIPAA Authorization should be given to the subject before participation in the trial. The original documents should be filed in the subject's study chart.

The initial informed consent form, any subsequent revised written informed consent form and any written information provided to the subject must receive the IRB's approval/favorable opinion in advance of use. The subject should be informed in a timely manner if new information becomes available that may be relevant to the subject's willingness to continue participation in the trial. The informed consent will adhere to IRB requirements, applicable laws, and regulations.

### **8.2.2 Assignment of Screening Number**

Once informed consent and HIPAA Authorization have been documented, the site will assign the subject a screening number. Each site will be responsible for maintaining their Screening Log of consented subjects.

### **8.2.3 Inclusion/Exclusion Criteria**

All inclusion and exclusion criteria will be reviewed by the investigator or qualified designee to ensure that the subject qualifies for the study.

### **8.2.4 Demographics**

Subject demographics will be obtained by the investigator or qualified designee.

### **8.2.5 Medical and Surgical History**

A medical and surgical history will be obtained by the investigator or qualified designee. Medical history will include all active conditions, and any condition deemed clinically relevant by the treating investigator. Surgical history will include any past surgeries deemed clinically relevant by the treating investigator.

### **8.2.6 Prior Medications**

The investigator or qualified designee will review prior medication use and record any medication taken by the subject within 21 days before signing the informed consent.

### **8.2.7 Concomitant Medications and Treatments**

The investigator or qualified designee will record any pain medication (including anti-inflammatories, NSAIDs, etc.), knee injections and surgeries the subject required during the study until the subject's final study visit.

### **8.2.8 Physical Examination**

Focused knee assessment will be performed. Please refer to the Operations Manual to ensure all required assessments are performed during the exam. At the 7-day follow-up and 30-day follow-up visits, the assessment will also include observation of the knee injection site for all subjects and observation of the harvest site for subjects in Arm 1 and Arm 2.

### **8.2.9 Vital Signs**

The investigator or qualified designee will obtain vital signs. Please refer to the Operations Manual for details.

### **8.2.10 MRI**

MRIs will be performed using cartilage mapping sequences for each location based on their machines. The baseline MRI scans and each subsequent MRI scan must be performed on the same machine with the same sequence. Further details are described in the MRI protocol.

### **8.2.11 Patient Reported Outcomes**

#### **8.2.11.1 Visual Analog Pain Scale (VAS)**

#### **8.2.11.2 Euro-Quality of Life (EQ5D 3L)**

#### **8.2.11.3 Knee Injury and Osteoarthritis Outcome Score (KOOS)**

#### **8.2.11.4 Patient-Reported Outcomes Measurement Information System (PROMIS 29)**

### **8.2.12 Adverse Event Monitoring**

The investigator or qualified designee will assess each subject to evaluate for potential new or worsening AEs at each study visit and more frequently if clinically indicated. Adverse experiences will be graded and recorded throughout the study according to CTCAE (Common Terminology Criteria for Adverse Events). Toxicities will be characterized in terms regarding seriousness, causality/attribution, toxicity grading, and action taken.

Subjects must agree to notify the investigator or study team member as soon as possible of any failure of proper use of your birth control method, or if a subject becomes pregnant, either of which may result in being withdrawn from the study or having limited participation in the study. Subjects who become pregnant while on the study will be followed for AEs/SAEs that may occur for up to 30 days following the birth of the child.

### **8.2.13 Physical Therapy**

Subjects will follow an at home physical therapy program, see Appendix 12.1, unless otherwise directed by the investigator. Instructions for the at home physical therapy will be provided to the subject, by the study team, at the treatment visit.

The study team will provide subjects with a physical therapy log to track compliance with the recommended daily activity (according to Appendix 12.1). Subjects will be required to return the log at the 7-day and 30-day follow-up visits. The study team will review the log for compliance.

### **8.2.14 Cell Characterization**

Cell characterization that will be performed includes:

- Cell viability assessment including apoptosis assay
- Cell phenotype assessment via comprehensive flow cytometry or mass cytometry
- Single-cell transcriptome analysis
- Secretome assessment from both initial aspirate and rescue culture supernatant

\*Specimen processing, storage and shipment details can be found in the Laboratory Manual.

### **8.2.15 Local Laboratory Assessments**

Laboratory assessments will be collected for subject safety.

#### **8.2.15.1 Hematology**

Hematology can be evaluated in either the fed or fasted state and consist of a complete blood count with differential count performed as needed at the investigator's discretion.

#### **8.2.15.2 Clinical Chemistry**

A comprehensive metabolic panel OR a basic metabolic panel and liver function panel will be evaluated in the fed or fasted state. Additional clinical chemistry testing will be performed as needed at the investigator's discretion. The subject's ALT and total bilirubin must be evaluated in order to determine study eligibility.

#### **8.2.15.3 Coagulation Assays**

Coagulation assays will be evaluated in the fed or fasted state and consist of prothrombin time (PT; sec) or international normalized ratio (INR). Activated partial thromboplastin time (APTT; sec) may be ordered at the discretion of the treating investigator.

#### **8.2.15.4 Immunogenicity Testing**

Immunogenicity Testing can be evaluated in either the fed or fasted state and consist of a panel reactive antibodies (PRA) on the recipient of the umbilical cord tissue at 30 days and at study completion. All subjects in Arm 3 will have a blood draw to maintain blinding.

#### **8.2.16 Pregnancy Testing**

Pregnancy testing for human chorionic gonadotrophin (hCG) will be performed on female subjects of childbearing potential (refer to eligibility criteria). This may be done using a urine or serum sample. Pregnancy testing will be done at two time points:

- a) **Screening Visit**- if the test is positive the subject will be a screen failure.
- b) **Treatment Visit** (prior to procedure/knee injection)- if the test is positive, within 7 days of the Treatment Visit, the subject will be discontinued from the study.

### **8.3 Protocol Deviations**

Assessments not performed at a required visit per protocol should be documented as a deviation from the protocol, regardless of the reason. When a protocol deviation occurs it should be discussed with the treating investigator and documented on the Protocol Deviation Form detailing the deviation. Protocol Deviation forms will be signed by the treating investigator and reviewed by the sponsor's representative.

### **8.4 Adverse Event Reporting and Safety Monitoring**

#### **8.4.1 Adverse Events**

An adverse event is defined as any untoward or unfavorable medical occurrence in human subject, including any abnormal sign, symptom, or disease, temporally associated with the subject's participation in the research, whether or not considered related to the subject's participation in the research.

The investigator or qualified designee will assess each subject to evaluate for potential new or worsening AEs as specified in the SoA and more frequently if clinically indicated. Adverse experiences will be graded and recorded throughout the study according to CTCAE.

#### **8.4.2 Serious Adverse Events**

If the adverse event meets any of the criteria below, it is regarded as a serious adverse event (SAE):

- a) Led to death
- b) Led to serious deterioration in the health of the subject, that either resulted in
  - a. A life-threatening illness or injury, or

- b. A permanent impairment of a body structure or a body function, or
- c. In-patient or prolonged hospitalization, or
- d. Medical or surgical intervention to prevent life-threatening illness or injury or permanent impairment to a body structure or a body function

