#### **8.4.3 AE and SAE Collection**

All AEs and SAEs will be collected from the signing of the informed consent form until the one-year follow-up visit at the time points specified in the SoA (Section 1.3) as required by applicable regulation and best practice.

All SAEs will be recorded and reported to the sponsor and the pharmacovigilance team at Advanced Clinical within 24 hours of the study personnel becoming aware of the event. Please utilize the approved SAE data collection forms provided by Advanced Clinical to submit the notifications and updates. The investigator will submit any updated SAE data to the sponsor within 24 hours of it being available.

Investigators are not obligated to actively seek AE or SAE after conclusion of the study participation. However, if the investigator learns of any SAE, including a death, at any time after a subject has been discharged from the study up to a 30 day follow-up period, and he/she considers the event to be reasonably related to the study intervention or study participation, the investigator must promptly notify the sponsor.

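### The SAE criteria in 8.4.2 omit congenital anomaly and leave fetal death unclear, although pregnancies are followed for AEs/SAEs until 30 days after birth, so a non-fatal birth defect does not trigger the 24-hour report

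*Combined protocol and SAP*

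**What the plan says.** **Seriousness (8.4.2).** An event is serious if it meets any one of the listed criteria. The first is death, without saying whose. The second is introduced by "Led to serious deterioration in the health of the subject, that either resulted in" and has four outcomes nested under it: life-threatening illness or injury, permanent impairment, hospitalization, and intervention to prevent the first two. The list ends there.

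**Adverse event (8.4.1).** The starting point for any SAE is "any untoward or unfavorable medical occurrence in human subject". Offspring are not mentioned.

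**Pregnancy (8.2.12, repeated in 9.4.4).** Subjects who become pregnant on study "will be followed for AEs/SAEs that may occur for up to 30 days following the birth of the child".

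**Reporting (8.4.3).** SAEs are to be "reported to the sponsor and the pharmacovigilance team at Advanced Clinical within 24 hours of the study personnel becoming aware of the event". AEs and SAEs are collected from consent to the one-year visit. After a subject leaves the study, the investigator must notify the sponsor only of SAEs judged reasonably related, and only those learned of within 30 days.

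**The concern.** Following a pregnancy past delivery makes the condition of the newborn an obvious thing to learn about. Yet the definition that decides what is urgent has no place for a birth defect. Two consequences are tied to the word SAE: the 24-hour report in 8.4.3 and the first halt trigger in 4.5, a potentially related SAE. An event that fits no criterion sets off neither. For fetal death the wording can be read either way, so two sites could classify the same event differently.

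Pregnancy is contemplated by the plan. Women of childbearing potential are eligible, contraception is required of women and men (5.1.1), and pregnancy is tested at screening and again before treatment (8.2.16). Section 2.3.1 also says that the risks of the autologous cell injections are not fully known.

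**Working it through.** No sample size, power or error rate is involved. The check reads each criterion against two outcomes, then compares the time windows.

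**1. Non-fatal birth defect, mother well**

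| Criterion in 8.4.2 | Met? | Reason |
|---|---|---|
| Death | No | Nobody died |
| Life-threatening illness or injury | No | Nested under the subject's health |
| Permanent impairment | No | Closest in content, but nested under the subject's health; the child is not the subject |
| Hospitalization | No | Same nesting |
| Intervention to prevent the above | No | Same nesting |

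The nearest item reads "A permanent impairment of a body structure or a body function, or". It would describe many birth defects if it stood alone, but it does not. With no criterion met, neither the 24-hour report nor the SAE-based halt applies.

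**2. Fetal death**

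- The death criterion does not name the subject, so it can be read as met.
- A miscarriage or stillbirth is itself an untoward occurrence in the pregnant subject, so it passes the AE definition in 8.4.1.
- It also qualifies if the mother's own deterioration is life-threatening, leads to hospitalization ("In-patient or prolonged hospitalization, or") or needs a qualifying intervention.
- If none of these applies to the mother, classification depends on how a site reads the death criterion. The result is ambiguous.

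**3. Time windows**

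Let conception fall c months after treatment, and assume a gestation of about 9 months (not in the documents).

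- Birth: c + 9 months.
- End of pregnancy follow-up (8.2.12): c + 9 + 1 = c + 10 months.
- End of routine collection (8.4.3): about month 12.
- End of the duty after discharge (8.4.3): about 12 + 1 = month 13, and only for related SAEs.

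Pregnancy follow-up outlasts routine collection when c + 10 > 12, that is, c > 2. The birth falls after both windows when c + 9 > 13, that is, c > 4. For conception at month 6, birth is at about month 15 and pregnancy follow-up ends at about month 16, against month 13 for the last duty in 8.4.3. Section 8.2.12 adds that pregnancy may lead to withdrawal, which could bring the end of participation forward. The duty after discharge also depends on the word SAE, so a birth defect would not start it even inside the window.

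**4. Other routes**

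| Route | Needs an SAE under 8.4.2? | 24-hour site duty? |
|---|---|---|
| Discretionary halt (4.5, second bullet) | No | No |
| AE reporting and review (8.4.5, 10.8) | No | No |
| Unanticipated-problem assessment (8.4.7) | No; covers risks to subjects or others | No |
| IND safety report (8.4.6) | Not stated; covers serious unexpected reactions without citing 8.4.2 | No; the sponsor's deadlines are 15 or 7 days |

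The routes in 8.4.5 and 8.4.7 start from an adverse event. Because 8.4.1 places the event in a human subject, a literal reader could keep a defect in the child out of both.

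**The case against.** The best reply is that the plan has more than one safety net. Section 4.5 allows a halt for any finding that the study team, DSMB, investigator or Medical Monitor considers sufficient. AEs go to the FDA, sponsor and IRB, and the Medical Monitor and DSMB review them. The unanticipated-problem wording can reach offspring. Reporting detail is delegated to SAE forms, the Operations Manual and the safety management plan, none of which is available here, so a pregnancy form or deadline may exist there. The protocol also never says that pregnancy follow-up is meant to detect birth defects; it speaks only of following subjects who become pregnant. Contraception, two pregnancy tests and a single treatment visit make such an event unlikely.

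Most of this stands, and it limits the point. A reader might infer that fetal death is excluded from the SAE list. It is not: the death criterion is unqualified, and a loss can qualify through the mother. A reader might also infer that such outcomes would reach no safety process at all. The documents do not support that either, given the routes above, and the dependence of IND safety reports on 8.4.2 is an inference.

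What the reply does not supply is a criterion in the protocol that a non-fatal birth defect meets, or a 24-hour duty on the site to report one.

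**Conclusion.** The point holds in limited form. Read as written, 8.4.2 classifies a non-fatal birth defect as not serious, and it leaves fetal death to interpretation. What is lost is the 24-hour site report and the automatic SAE-based halt trigger; slower or discretionary routes remain. The collection window in 8.4.3 and the pregnancy follow-up in 8.2.12 also do not match.

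The expected count is small. The plan gives no pregnancy figure, so low numbers at ages 40 to 70 are an assumption. No efficacy analysis is affected, nor is the infection and allergy boundary in 9.4.3. The conclusion rests on the protocol text alone and would soften if the Operations Manual or safety management plan already sets a pregnancy reporting deadline. Because the stated rule itself gives the wrong classification, correcting the text is worthwhile even for a rare event.

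**What to change.** 1. **8.4.2:** add a criterion for congenital anomaly or birth defect in a subject's offspring, and state explicitly that fetal death is covered.
2. **8.4.1:** extend the AE definition so that these outcomes can enter it. Without this, the new criterion would sit behind a definition that does not reach the child.
3. **8.2.12 and 9.4.4:** cross-refer to the 24-hour report in 8.4.3.
4. **8.4.3:** reconcile the collection window (one-year visit, then 30 days for related SAEs) with the pregnancy follow-up period.
5. Check the Operations Manual, safety management plan and SAE forms for an existing pregnancy procedure and make them agree.

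The cost is wording changes in five protocol sections and the SAE form instructions, plus a few more expedited reports. A birth defect judged potentially related would then also fall under the existing SAE trigger in 4.5, which the sponsor should note when making the change. Sample size and efficacy analyses are untouched.
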